#### **11.1.5.4.2. Monitoring and Management of Elevated Serum Creatinine**

If at any time after randomization, a patient experiences a decrease in eGFR to the level of  $15 \text{ mL/min}/1.73 \text{ m}^2$  or if the patient experiences acute renal failure, the patient should be withdrawn from IMP treatment but will be asked to continue to be followed for safety using the protocol-specified visit schedule (see [Appendix 1](#))

#### **11.1.5.4.3. Monitoring and Management of Elevated Creatine Kinase**

If at any time after randomization a patient experiences a marked CK elevation  $>5 \times \text{ULN}$ , the patient will undergo repeat confirmatory assessment as soon as is reasonably possible, preferably within 3 to 7 days of the laboratory result becoming available.

Repeat CK assessment will include query for related symptoms.

- If the repeat CK assessment confirms an unexplained (ie, not associated with recent trauma or physically strenuous activity) CK abnormality  $>5 \times \text{ULN}$ , if asymptomatic, the patient should receive further assessment and investigation into the cause, assess whether there is renal injury, and measure CK approximately weekly or more frequently if clinically indicated until resolution. If CK levels continue to rise; IMP should be discontinued.
- If symptomatic, the following should be completed:
  - Hold IMP
  - Clarification of the nature, duration, and intensity of muscle symptoms
  - Review possible predisposing factors, such as unaccustomed exercise, heavy alcohol intake, viral illness (consider performing serology)
  - Evaluation for additional diagnoses or other conditions which can cause myopathy including muscle tenderness (by PE), weakness, rash, measurement of serum creatinine, dipstick urinalysis with microscopy if indicated
  - Obtain clinical chemistries to assess the possibility of lactic acidosis
  - Follow symptoms and CK until the abnormality has resolved
  - If based on the above evaluation an alternative explanation is suspected, consideration can be given to resuming IMP once CK returns to baseline levels
  - If no alternative explanation exists, consideration should be given to withdrawing the patient from IMP treatment.
- If the repeat CK assessment confirms an unexplained (ie, not associated with recent trauma or physically strenuous activity) CK abnormality as listed below, the patient should be withdrawn and given no further doses of study drug:
  - $>10 \times \text{ULN}$ , even in the absence of symptoms.
  - In all cases, evaluate the signs/symptoms and laboratory evaluations as outlined above.

- If the patient is withdrawn from IMP treatment, the patient should be asked to continue being followed for safety using the protocol-specified visit schedule (see [Appendix 1](#)).

#### **11.1.5.5. Monitoring and Management of Potential Hypoglycemia and Metabolic Acidosis**

Patients will be educated on the signs and symptoms of hypoglycemia. If such signs and symptoms are experienced, patients will be instructed to report these signs and symptoms to the investigator.

During each study visit, patients will be reminded to report all signs and symptoms associated with hypoglycemia to the investigator. For each occurrence of patient-reported signs and symptoms associated with hypoglycemia, the investigator will discuss these symptoms with the patient and assess whether they are attributable to hypoglycemia or to another potential cause. All investigator-confirmed occurrences of hypoglycemia will be recorded as an AE. All occurrences of signs and symptoms that are not confirmed by the investigator to be attributable to hypoglycemia will be reported using the appropriate diagnosis.

Clinical laboratories will be assessed to determine any signs of anion gap metabolic acidosis. If laboratories are consistent with metabolic acidosis, immediate follow up with the patient for further medical evaluation of the acidosis will occur. This event should be captured as an AE.

## **12. ADVERSE AND SERIOUS ADVERSE EVENTS**

### **12.1. Adverse Events**

#### **12.1.1. Definition of Adverse Events**

An AE is defined as any untoward medical occurrence in a clinical investigation patient administered a pharmaceutical product, including control, and which does not necessarily have a causal relationship with treatment. The investigator is responsible for ensuring that any adverse events observed by the investigator or reported by the patient are recorded in the patient's medical record.

An AE can be:

- Any unfavorable and unintended sign/symptom, including an abnormal laboratory finding, or disease temporally associated with the use of a medicinal product, whether or not considered related to the medicinal product
- Any new disease or exacerbation of an existing disease
- Laboratory abnormality or diagnostic test abnormalities (eg, x-ray) should be reported as an AE if one of the following occurs
  - Treatment required due to the abnormality
  - Discontinuation of IMP
  - Per Investigator judgement
- TEAEs are defined as AEs that begin or worsen after the first dose of study drug administration, as defined in the Statistical Analysis Plan (SAP).

#### **12.1.2. Adverse Drug Reaction**

All noxious and unintended responses to a medicinal product related to any dose should be considered an adverse drug reaction (ADR). "Responses" to a medicinal product means that a causal relationship between the medicinal product and an AE is at least a reasonable possibility (ie, the relationship cannot be ruled out).

An unexpected ADR is defined as an adverse reaction, the nature or severity of which is not consistent with the applicable product information (eg, IB for an unapproved investigational product or package insert/summary of product characteristics for an approved product).

#### **12.1.3. Reporting for Adverse Events**

All AEs occurring during the course of the study (starting from signing informed consent through 30 days after last dose of study treatment) will be collected on the AE eCRF. Patients should be instructed to report any AE that they experience to the investigator. Investigators should make an assessment for AEs at each visit and record the event on the appropriate AE eCRF.

Wherever possible, a specific disease or syndrome rather than individual associated signs and symptoms should be identified by the investigator and recorded on the eCRF. A cluster of signs and symptoms that results from a single cause should be reported as a single AE (eg, fever, elevated white blood cells [WBC], cough, abnormal chest x-ray, etc, can all be reported as “pneumonia” if that is the final diagnosis). However, if an observed or reported sign or symptom is not considered a component of a specific disease or syndrome by the investigator, it should be recorded as a separate AE on the eCRF. Additionally, the condition that led to a medical or surgical procedure should be recorded as the AE, not the procedure itself.

Any medical condition already present at screening or baseline should not be reported as an AE unless the medical condition or signs or symptoms present at baseline worsens in severity or seriousness at any time during the study. In this case, it should be reported as an AE.

Clinically significant abnormal laboratory or other examination findings that are detected during the study or are present at baseline and significantly worsen during the study should be reported as AEs, as described below. The investigator will exercise his or her medical and scientific judgment in deciding whether an abnormal laboratory finding or other abnormal assessment is clinically significant. Significant abnormal laboratory values occurring during the clinical study will be followed until repeat tests return to normal, stabilize, or are no longer clinically significant. Any abnormal test that is determined to be an error does not require reporting as an AE.

An abnormal laboratory value that is not already associated with an AE is to be recorded as an AE only if any one of the following criteria is met:

- an action on the study drug is made as a result of the abnormality
- intervention for management of the abnormality is required
- at the discretion of the investigator should the abnormality be deemed clinically significant

Each AE is to be evaluated for duration, severity, seriousness, and causal relationship to the IMP. For each AE, the following information will be recorded:

- Description of the event (eg, headache)
- Date of onset
- Date of resolution (or that the event is continuing)
- Action taken as a result of the event
- Seriousness of the event
- Severity of the event
- Outcome of the event
- Investigator’s assessment of relationship to IMP or PCSK9i.

The investigator will carefully evaluate the comments of the patient and the response to treatment in order that he/she may judge the true nature and severity of the AE. The question of

the relationship of AEs to IMP administration should be determined by the investigator or study physician after thorough consideration of all facts that are available.

#### **12.1.4. Severity**

It is the investigator's responsibility to assess the intensity (severity) of an AE.

The severity of the AE will be characterized as mild, moderate, or severe according to the following definitions:

- Mild: Events are usually transient and do not interfere with the patient's daily activities
- Moderate: Events introduce a low level of inconvenience or concern to the patient and may interfere with daily activities
- Severe: Events interrupt the patient's usual daily activity, are incapacitating with inability to do usual activities, or significantly affect clinical status and warrant intervention and/or close follow-up

Note: A severe AE need not be serious and an SAE need not, by definition, be severe.

#### **12.1.5. Relationship**

It is the investigator's responsibility to assess the relationship between the IMP and the AE. The degree of "relatedness" of the AE to the IMP may be described using the following scale:

- Not Related: No temporal association and other etiologies are likely the cause
- Unlikely: While cannot be definitively ruled as not related to IMP, a causal association is remote, and other etiologies are more likely to be the cause. For reporting and summarization, events assessed as Unlikely to be related to IMP will be considered as Not Related to IMP.
- Possible: Temporal association, but other etiologies are likely the cause. However, involvement of the IMP cannot be excluded.
- Probable: Temporal association, other etiologies are possible but unlikely. The event may respond if the IMP is discontinued.
- Definite: Established temporal association with administration of the IMP with no other more probable cause. Typically, the event should resolve when the IMP is discontinued and recur on rechallenge.

#### **12.1.6. Monitoring and Follow-up of Adverse Events**

Patients having AEs will be monitored with relevant clinical assessments and laboratory tests, as determined by the investigator. All follow-up results are to be reported to the Sponsor personnel or the authorized Medical Monitor. Any actions taken and follow up results must be recorded either on the appropriate page of the eCRF or in appropriate follow-up written correspondence, as well as in the patient's source documentation. Follow-up laboratory results should be filed with the patient's source documentation.

For all AEs that require the patient to be discontinued from the study, relevant clinical assessments and laboratory tests must be repeated at appropriate intervals until final resolution or stabilization of the event(s).

Patients with AEs related to IMP that are ongoing at study discontinuation or completion must be followed until resolution, until deemed stable/chronic, or for 30 days after study completion, whichever comes first, with the exception of patients reporting SAEs (see [Section 12.2.2](#)).

### **12.1.7. Treatment-Emergent Adverse Events**

TEAE are defined as AEs that begin or worsen after the first dose of study drug administration, as defined in the SAP.

## **12.2. Serious Adverse Events**

### **12.2.1. Definition of Serious Adverse Event**

An SAE is defined as any AE occurring at any dose that results in any of the following outcomes:

- Results in death
- Is life threatening
- Requires inpatient hospitalization or prolongation of existing hospitalization
- Results in persistent or significant disability/incapacity, or substantial disruption of the ability to conduct normal life functions
- Is a congenital anomaly/birth defect
- An important medical event

NOTE: An emergency room visit without hospital admission does not meet inpatient hospitalization criteria, nor does hospitalization for an elective or outpatient procedure scheduled or planned before signing of informed consent. However, unexpected complications and/or prolongation of hospitalization that occur during elective or outpatient surgery should be recorded as AEs and assessed for seriousness. Admission to the hospital for social or situational reasons (eg, no place to stay, live too far away to come for hospital visits) will not be considered inpatient hospitalizations.

Important medical events that may not result in death, be life threatening, or require hospitalization may be considered an SAE when, based upon appropriate medical judgment, they may jeopardize the patient and may require medical or surgical intervention to prevent one of the outcomes listed in this definition. Examples of such medical events include allergic bronchospasm requiring intensive treatment in an emergency room, blood dyscrasias, convulsions that do not result in inpatient hospitalization, or the development of drug dependency or drug abuse.

### **Events or Outcomes Not Qualifying as Serious Adverse Events**

The following are not considered SAEs and therefore do not need to be reported as such:

- Preplanned or elective hospitalization, including social and/or convenience situations (eg, due to inclement weather)
- Overdose of either Esperion study drug or concomitant medication unless the event meets SAE criteria (eg, hospitalization). However, the event should still be captured as a nonserious AE on the appropriate eCRF page

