#### **12.2.2. Reporting Serious Adverse Events**

All SAEs occurring from the time of informed consent until 30 days following study completion/discontinuation must be reported by the Principal Investigator or designee to the designated Safety contact within 24 hours of knowledge of the event. All SAEs that the investigator considers related to IMP that occur after the 30-day follow-up period of the study period must be also reported to the Sponsor.

To report the SAE, the SAE information should be entered on to the AE eCRF in the EDC database within 24 hours of becoming aware of the event. If you have questions, please call the designated Safety contact for assistance.

Detailed instructions and contact information for the Safety designee will be provided in the SAE Completion Guidelines.

The investigator is required to submit SAE reports to their IRB/IEC in accordance with local requirements. All investigators involved in studies using the same investigational product will receive any safety alert notifications for onward submission to their local IRB as required. All reports sent to investigators will be blinded.

All SAEs should be recorded on the eCRF and source documents. Criteria for documenting the relationship to IMP and severity will be the same as those previously described.

The investigator must continue to follow the patient until the SAE has subsided or until the condition becomes chronic in nature, stabilizes (in the case of persistent impairment), or the patient dies.

Within 24 hours of receipt of follow-up information, the investigator must update the SAE information on the AE eCRF and submit any supporting documentation (eg, patient discharge summary or autopsy reports) to designated Safety contact.

The Sponsor (and/or legally transferred designee) will report SAEs and suspected and unexpected serious adverse reactions (SUSARs) as required by global regulatory authorities, IECs/IRBs, and/or investigators/institutions in compliance with all reporting requirements according to local regulations, laws, and Good Clinical Practices (GCPs). The investigator should notify their IEC/IRB of SAEs occurring at their site and other SAE reports received from the Sponsor, in accordance with local procedures and statutes.

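### Protocol Section 12.2.1 and the exclusion list that follows it set different limits on elective hospitalization, so the SAE status of an elective admission arranged after consent for a new condition is unsettled.

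*Protocol*

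**What the plan says.** Protocol Section 12.2.1 gives six outcomes that make an AE serious. One is "Requires inpatient hospitalization or prolongation of existing hospitalization". A note then narrows this criterion. An emergency room visit without admission does not meet it, "nor does hospitalization for an elective or outpatient procedure scheduled or planned before signing of informed consent". The note also removes admissions for social or situational reasons, and it requires unexpected complications or a prolonged stay during elective surgery to be recorded and assessed for seriousness.

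The list headed Events or Outcomes Not Qualifying as Serious Adverse Events comes next. It opens with "The following are not considered SAEs and therefore do not need to be reported as such". Its first item is "Preplanned or elective hospitalization, including social and/or convenience situations (eg, due to inclement weather". Its second item is "Overdose of either Esperion study drug or concomitant medication unless the event meets SAE criteria (eg, hospitalization", so overdose carries an exception that the hospitalization item lacks.

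Section 12.2.2 sets the reporting period: "All SAEs occurring from the time of informed consent until 30 days following study completion/discontinuation must be reported". The report is due within 24 hours of the site learning of the event. The SAP tabulates SAEs (Sections 5.4 and 5.4.1), but its text does not define one.

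**The concern.** The two texts are consecutive, both are in force, and they draw the line in different places. The note asks when the procedure was planned relative to consent. The list asks only whether the admission was preplanned or elective. It names no reference point for the planning, and the word joining the two terms brings in elective admissions that were not preplanned.

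A site that follows the list literally could leave the seriousness box unticked for a patient who develops a new illness on study and is booked for a scheduled admission. Several steps depend on that box:

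- the 24-hour report and the onward reporting by the sponsor (Section 12.2.2);
- follow-up, because Section 12.1.6 lets follow-up of an ongoing drug-related AE end 30 days after study completion but excepts SAEs, which Section 12.2.2 follows until they subside, stabilize or become chronic, or the patient dies;
- the SAE tables and listings in the SAP.

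With about 20 sites, the same event could also be classified differently from one site to the next.

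**Working it through.** The plan gives no figure to reproduce here. The check is a comparison of the two texts, case by case, followed by simple arithmetic for size.

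**Step 1. Is the underlying event an AE?** Section 12.1.1 counts "Any new disease or exacerbation of an existing disease" as an AE. Section 12.1.3 says the condition leading to a procedure is recorded as the AE, not the procedure. So a new condition is on the AE form under either text, and only its seriousness is open.

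**Step 2. Apply both texts to each type of admission.**

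| Admission | Section 12.2.1 with its note | Not Qualifying list | Agree? |
|---|---|---|---|
| Elective, planned before consent, uneventful | Exempt | Exempt | Yes |
| Social or convenience | Exempt | Exempt | Yes |
| Elective, arranged after consent, with a complication or another seriousness criterion met | Assessed on the complication or the other criterion | The item exempts the hospitalization, not the other criteria | Yes |
| Elective, arranged after consent for a new condition, no complication, no other criterion met | Meets the hospitalization criterion and falls outside the pre-consent exemption: SAE by inference | Elective, so not an SAE and not reported as one | **No** |

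The conflict is confined to the last row.

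**Step 3. Is that case inside the reporting period?** Yes. Section 12.2.2 runs from consent to 30 days after completion or discontinuation, so an admission arranged after consent falls within it.

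**Step 4. Size.** Inputs: 26 patients per arm (Protocol Section 13.2); Month 2 visit at Day 61 and screening at Day -135 (Appendix 1); 30 days of follow-up (Section 12.2.2).

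- Effect of one event on one arm: 1 / 26 = 0.038, or 3.8 percentage points. This assumes that all 26 patients in the arm are dosed and so enter the safety population.
- Post-randomization window: 61 + 30 = 91 days.
- Whole collection period: 135 + 61 + 30 = 226 days, of which 135 / 226 = 60% precedes randomization.

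Only the 91 days bear on the comparison between arms. SAP Section 5.4 defines treatment-emergent events from the first double-blind dose and summarizes run-in AEs as one overall group.

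**The case against.** The best defence is that the contradiction is inferred. Section 12.2.1 never states that an elective admission arranged after consent is an SAE. That follows from the hospitalization criterion combined with an exemption that stops at consent. The list item sits directly below the note and mentions social and convenience situations, so it can be read as shorthand for the note's two exemptions. Both observations are fair. But the consent qualifier does no work unless later elective procedures fall outside the exemption, and nothing in the wording of the list imports it. The narrow reading is possible; the text does not require it.

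It can also be said that the SAE Completion Guidelines, to which Section 12.2.2 refers for detailed instructions, may already settle the matter. That document is not available here. Even if it does, the protocol should not contradict itself.

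The affected case is narrow, and safety is described without statistical inference (Protocol Section 13.7), so no test or decision rule changes. That stands, and it limits the weight of the point.

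A reader might infer more than the documents support:

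- **That the event is lost or hidden from the Data Monitoring Committee.** AEs and SAEs go on the same form (Section 12.2.2), and the committee reviews accumulating safety data, with SAEs in addition (Section 12.4). The event could be missing from the SAE data, but not from the safety data.
- **That a serious illness becomes non-serious simply because the admission was scheduled.** This happens only if hospitalization is the sole criterion met. Death, threat to life, disability and the important-medical-event criterion still apply, as does the assessment of complications.
- **That the 3.8-point shift applies over all 226 days.** The 135 days before randomization do not enter the treatment-emergent comparison.

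**Conclusion.** The protocol is inconsistent as written. For an elective admission arranged after consent, for a new condition, with no complication and no other seriousness criterion, Section 12.2.1 leads to an SAE and the list leads to an exemption. No other text in the protocol or SAP resolves it.

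The consequence is limited to classification and what follows from it: the flag, the 24-hour report, the length of follow-up and the SAE counts. One affected event after randomization changes an arm's SAE incidence by 3.8 points. That figure is the weight of any single event in an arm of 26. It does not say how likely such an event is, and the documents give no basis for estimating that.

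The conclusion rests on reading the list as it is worded and on treating the pre-consent qualifier in the note as deliberate. The documents do not show which scope the sponsor intended. Appendix 4 (Change 19) shows that Amendment 1 added the list and kept the note, which explains how two rules came to stand together but not which should govern.

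**What to change.** Reconcile the two texts so that both carry the same limit on elective hospitalization. One way that needs no new concept is to carry the pre-consent qualifier already in Section 12.2.1 into the hospitalization item of the list. Make social and convenience admissions a separate item, so that the qualifier does not attach to them. Then check that the SAE Completion Guidelines say the same.

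A further condition, that the underlying illness has not worsened since consent, might seem a natural addition. It is in neither text and is not needed to remove the conflict; Section 12.1.3 already makes worsening of a pre-existing condition an AE.

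The cost is one edited bullet, one new bullet and a check of the guidelines. If the pre-consent limit is adopted, the downside is possibly a few more SAE reports. The analysis methods in the SAP do not change.
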